**Milestones:**

Draft protocol: July 31 2015

Submission to SC: August 6, 2015

Comments from SC: August 31, 2015

Submission for consortium review: September 2015

Submission to in house clearances/ governance boards: January 2016

Updated protocol after review: April 15, 2016

Final data extraction to CDM: June 15, 2016

Running scripts and submission to RRE: June 30, 2016

Data analysis: July 2016

Data interpretation and reporting: August 2016

Final report of study results: September 2016

---

### 3. AMENDMENTS AND UPDATES

Protocol amendments following IRB approval:

**Table 2: Overview of Protocol Amendments and Updates**

Number	Date (DDMMYY)	Section of the study protocol	Amendment or update	Reason
1				
2				
....				

### 4. MILESTONES

**Table 3: Overview of Study Milestones**

Draft protocol: July 31 2015

Submission to SC: August 6, 2015

Comments from SC: August 31, 2015

Submission for consortium review: September 2015

Submission to in house clearances/ governance boards: January 2016

Updated protocol after review: April 15, 2016

Final data extraction to CDM: June 15, 2016

Running scripts and submission to RRE: June 30, 2016

Data analysis: July 2016

Data interpretation and reporting: August 2016

Final report of study results: September 2016

---

## 5. RATIONALE AND BACKGROUND

The ADVANCE vision is to deliver “best evidence at the right time to support decision-making on vaccination in Europe”. The mission is to establish a prototype of a sustainable and compelling system that rapidly provides best available scientific evidence on vaccination benefits and risks post-marketing for well-informed decisions. In light of this goal, the ADVANCE platform aims to provide evidence on the benefits and risks of vaccines to support decision-making by all stakeholders in a wide range of contexts. Examples of scenarios are the inclusion of a new vaccine in a vaccination program, and the occurrence of a new safety issue, e.g. when the benefits of the vaccine are questioned or when a new population is targeted (see Pertussis POC Outline).

The concept this POC feasibility study aims to demonstrate is as follows: in the event that an important decision regarding a health intervention is to be made, a benefit-risk assessment will be carried out. Upon a favorable benefit-risk assessment, the health intervention is implemented and the benefits and risks are monitored to investigate whether the benefit-risk balance is changing over time. The benefit-risk monitoring may focus primarily on the benefits and risks that could potentially modify the benefit-risk balance. If there is a strong indication that the benefit-risk has changed over time, a full re-assessment of the benefit-risk balance of the health intervention may be triggered using all accumulated evidence available at that point in time. To inform the benefit-risk assessment and monitoring, electronic health care databases available within Europe will be used.

To be able to prove this concept of benefit-risk monitoring in ADVANCE without waiting for the evidence to accumulate prospectively, we will start from a historical decision and simulate monitoring through a retrospective analysis. Pertussis vaccination, particularly comparing wP and aP vaccination, was chosen by the ADVANCE Steering Committee as the subject of the first POC feasibility study. Therefore, the starting point of the current POC feasibility study is the historical decision to switch from wP to aP vaccination in children in the pioneering countries.

[figure not shown]
### **PERTUSSIS DISEASE**

Pertussis, also referred to as whooping cough, is a highly contagious respiratory disease caused by bacteria of the *Bordetella* genus, mainly *B. pertussis*, although other *Bordetella*-species also occur [1,2]. Pertussis is acquired through transmission of large respiratory droplets generated by coughing or sneezing from infected persons [3].

Transmission by the indirect route occurs extremely rarely if ever [4]. *B. pertussis* causes respiratory symptoms, along with systemic effects, presumably mediated by secreted toxins [4]. Infections range in clinical presentation from asymptomatic to severe. They are most severe, even life-threatening, in young infants before they are immunized [5]. It is less frequently severe in older children, adolescents, and adults.

---

 This section is obtained from the POC outline:  
[https://www.dropbox.com/s/ioru753h9h8cy44/240315\\_POC%20pertussis%20outline\\_version%201.5\\_tob\\_edistributed.docx?dl=0](https://www.dropbox.com/s/ioru753h9h8cy44/240315_POC%20pertussis%20outline_version%201.5_tob_edistributed.docx?dl=0)

**Figure 1:Graphic Representation of Time Axes/Horizons**

For the study, a retrospective approach is taken (i.e. all benefits and risks to be measured have already occurred). For the decision analysis, benefits and risks will be compared between wP and aP. The evidence for wP vaccines has been accumulated mostly prior to the switch, with some data coming afterwards from the last vaccinated persons. Evidence from aP vaccines at the time of the switch comes mostly from clinical data and is complemented by post-marketing data after the switch. The arrows in Figure 1 show that the increasing amount of evidence on benefits and risks for wP and aP will be cumulatively assessed from the time of the switch. The upper part represents the time frame for the study subjects; these will be followed from start of the study period, one month after date of birth (i.e. to allow for pre-vaccination time for the SCCS design and to avoid pre-term related or birth-induced increase in incidence rates), or date of valid data in the database (whichever is the latest) until the end of study period (31-12-2015, the school-entry pertussis booster, transference out of the database, death, attainment of age 6 years: whichever is the earliest). Rates and risks of benefits and risks will be assessed by type and dose of aP or wP. Note: the primary vaccination series in infancy follows a '2+1' or '3+1' schedule, depending on country.

Typical clinical disease is characterized by three phases. After 7-28 days of incubation, the catarrhal phase (1-2 weeks) is largely nonspecific with coryza, eye redness, frequent coughing and sneezing. It is followed by a 1-6 week-long paroxysmal phase during which intense paroxysms of cough may lead to choking, emesis and the characteristic inspiratory whoop [3]. In very young infants, cough is often absent and apnea seems more characteristic of the disease [6]. Fever is rare in pertussis. The convalescent phase sees declining symptoms over widely variable duration [3].

Clinical criteria for the diagnosis of pertussis include a cough lasting at least two weeks and at least one of the following three: paroxysms of coughing, inspiratory 'whooping', and/or post-tussive vomiting; or any person diagnosed as pertussis by a physician, or apnoeic episodes in infants.

Pertussis infection may be followed by common but usually self-limiting complications such as apnea, seizures, vomiting, gastroesophageal reflux, rib fracture, subconjunctival hemorrhages, epistaxis or

---

syncope secondary to the paroxysms [4,5]. According to the Institute of Medicine report, apnea and respiratory arrest are the most common complication of pertussis followed by pneumonia and gastroesophageal reflux. Encephalopathy is a rare complication and occurs most often in younger patients. Other complications include seizures, ataxia, aphasia, blindness, deafness, subconjunctival hemorrhages, syncope, and rib fractures. Pertussis is most serious in infants less than 12 months of age, and the risk of death is highest among infants less than 6 months old.

### **TYPE OF PERTUSSIS VACCINES**

Vaccines against pertussis were developed in the 1920s and have been used more widely since the 1940s [7]. The first vaccines were wP vaccines containing suspensions of killed *B. pertussis* organisms [4]. The production process varied between different wP vaccines, resulting in differences in antibody responses. Furthermore, due to the use of the whole bacterium, composition and thus immunogenicity, efficacy and reactogenicity of a specific wP vaccine could change over time, from lot to lot within one wP vaccine, and from one wP vaccine to another. Reactogenicity of the wP vaccine is probably due to their endotoxin lipopolysaccharide (LPS) content [8]. In an attempt to reduce reactogenicity, aP vaccines were developed. They were used for the first time in 1981 during mass vaccination campaigns in Japan [9], and more widely during and since the 1990s. aP vaccines contain purified secreted and surface components of *B. pertussis* which, based on animal models, are thought to play an important role in pathogenesis and induction of immunity [4]. Later on, several aP vaccines were manufactured, containing between one and five different pertussis components [2].

All aP vaccines contain at least a detoxified pertussis toxin (PT); the second antigen added in all formulations with two or more components is filamentous haemagglutinin (FHA); three-component vaccines contain also pertactin (PRN); finally, four- and five-component vaccines contain one or more fimbrial agglutinogens or fimbriae (FIM). Almost all aP vaccines are adjuvanted with aluminium salts and combined with diphtheria and tetanus toxoids, and possibly also additional vaccine valences such as inactivated poliovirus, *Haemophilus influenzae* type b and/or hepatitis B [4].

### **PERTUSSIS VACCINATION SCHEDULES IN EUROPE**

Between 2004 and 2015 several countries switched from wP to aP vaccines for infants and children. All other countries in Europe switched to aP vaccines prior to 2006 (starting in the 1990s for some countries). As of March 2015, all countries except Poland use exclusively aP vaccines. In most cases, the switch to aP vaccines was conducted over a narrow age-cohort, while only in very few cases, such as Poland, the switch occurred, or is occurring progressively over years. Different types of vaccines are being used. As part of the coverage pillar the way participating countries switched should be described.

Since the start of the introduction of pertussis vaccine in the 1940s, many countries have tended to adapt and customize the schedules of their vaccination programs, adding and removing doses, changing ages of primary and booster schedules, with or without catch-up campaigns, and transitioning from wP to aP vaccines for all doses, for one or more booster doses only, or not yet at all. As a result, pertussis vaccine schedules vary largely across Europe.

For detailed information on the schedules currently used in Europe, see Figure 2 and for more details see European Centre for Disease Prevention and Control (ECDC)-website (<http://vaccine-schedule.ecdc.europa.eu/Pages/Scheduler.aspx>).

---

 [http://www.nap.edu/openbook.php?record\\_id=13164&page=529](http://www.nap.edu/openbook.php?record_id=13164&page=529)

Schedule type	First year of life			Second year of life	Third year of life	Preschool booster	Adolescent booster	Country
	From 6 weeks to 6 months		Around first birthday					
'2p+1'	P1	P2	B1			B2	B3	F, IT, FI, NO, IS, SK
								SE, DK, RO, AT
'3p+1'	P1	P2	P3	B1		B2	B3	BE, BG, CZ, EE, DE, GR, HU, LI, LU,
				B1		B2		HR, CY, LV, LI, MT, NL, PL, PT, SI, ES
					B1			UK
						B1	B2	IE
Vaccine combination generally used in EU/EEA	
 
DTaP-IPV-HepB/Hib ('hexavalent')
 
DTaP-IPV/Hib ('pentavalent')
 
DTaP-IPV ('tetraivalent')
 
DTwP-IPV/Hib ('whole-cell pertussis combo')
 
Hep B (used in conjunction with pentavalent)
 
			
 
Hib-MenC combo
 
	
 
DTaP-IPV
 
Tdap
 
Tdap-IPV
 
Tdap
 
	
 
Td
 
Tdap
 
Tdap-IPV
 
		

P=primary dose; B=booster dose

**Figure 2: Recommended Pertussis Schedules from ECDC Report on Pertussis Vaccine Shortage (October 2015)**

The World Health Organization (WHO) standards of childhood pertussis vaccination recommend a three-dose primary series administered between 6 weeks and 6 months of age, followed by a booster dose, preferably in the second year of life. As previously mentioned, various countries have adapted and customized their vaccination schedules according to their policy considerations. As of March 2015, 19 countries use a three-dose schedule for the primary series, either at 2-3-4 months of age (n=9) or 2-4-6 months of age (n=10). Most of these countries give a toddler booster dose towards the end of the first year of life (n=3) or during the second year of life (n=13). In one country this booster dose can be administered before or after the first birthday; two countries do not recommend any toddler booster dose. Seven countries administer a two-dose primary series at three and five months of age, followed by a booster for 12 month-olds. Only France has a two-dose schedule at two and four months of age followed by a booster at 11 months of age.

All countries, except Malta, recommend one (n=11), two (n=15) or three (n=4) further aP booster doses between two and 18 years of age.

Six countries recommend one or more aP booster doses for all adults and/or elderly. Two countries (United Kingdom and Ireland) only target pregnant women in their last trimester of pregnancy (since late 2012).

## VACCINE RISKS

### Safety Studies

In a study including 15,752 doses of diphtheria, tetanus, whole cell pertussis (DTwP) vaccine and 784 doses of diphtheria, tetanus (DT) vaccine performed in the Los Angeles area in 1978-1979, local redness, swelling and pain occurred in 37.4%, 40.7% and 50.9% of DTwP recipients compared with 7.6%, 7.6% and 9.9% of DT recipients, respectively. Frequencies increased in subsequent doses. Frequency of fever ( $\geq 38^\circ\text{C}$ ) was 46.5% and 9.3% after DTwP and DT, respectively. Furthermore, high-pitched unusual crying, convulsions and HHE following DTwP were reported in 0.1%, 0.06% and 0.06% recipients, respectively. Those events were not reported after DT, probably due to the low number of DT vaccinees [3].

---

A large study, performed in the USA, assessed common reactogenicity of 13 candidate aP vaccines compared to wP vaccine. For all adverse events following immunization (AEFIs), frequencies after aP vaccines were lower than after wP vaccines. For fever ( $\geq 37.8$  °C) frequency was 4.2% after the first dose of aP vaccine compared with 27.3% following wP vaccination. Temperature increased after subsequent doses. Incidence of local redness was 13.5% and 49.4%, local swelling was 8.7% and 39.7%, and local pain was 3.8% and 27.3% after aP and wP vaccination, respectively [10].

For rarer and more severe AEFIs, frequencies also differed. Persistent crying, very high fever ( $\geq 40.5$  °C), HHE and seizures were respectively 7, 7, 17 and 6 times more likely after vaccination with wP compared with aP [11].

In a large (n=28,796) questionnaire study carried out in the Netherlands between 2004 and 2007, frequencies of rarer, more severe AEFIs were higher after the Dutch wP vaccine (used until 2005) compared with the aP vaccine (introduced from January 1st 2005 onwards) [12]. In total, 1.5% of the infants reported prolonged crying  $\geq 3$  hours after first dose at two months after wP vaccination compared with 0.4% after aP. Frequencies of very high fever ( $\geq 40.5$  °C) after the fourth dose of wP and aP vaccines at 11 months were 0.8% and 0.2%, respectively, whereas frequencies for febrile convulsions after the fourth dose were 0.06% and 0.02%, and for HHE after the first dose were 0.12% and 0.03%, respectively.

A review by Jefferson et al showed that wP vaccines were associated with a significantly higher incidence of swelling and induration (odds ratio [OR] 11.7; 95% confidence interval [CI] 8.8-15.4), fever  $>39$  °C (OR 3.4; 95% CI 2.1-5.5) and crying for  $>2$  hours (OR 4.7; 95% CI 2.9-7.6) than placebo or DT-vaccinations without a pertussis component. Differences in the incidence of HHE and convulsions were not statistically significant. aP vaccines did not cause a higher incidence of local signs, fever, convulsions, HHE or prolonged crying than placebo or DT vaccine [13].

Permanent damage to the central nervous system was repeatedly reported as 'causally related' to wP vaccines [14]. However, the National Childhood Encephalopathy Study and a consecutive huge body of scientific evidence eventually showed there was no association between neurological sequelae and wP vaccines [15,16]. However, these concerns were behind the motivation to develop aP vaccines.

In an observational study evaluating the safety of hexavalent vaccines (DTaP-IPV-Hib-HepB) involving 78 preterm infants, immunization triggered transient cardiorespiratory events in 47% of infants (15% apnoea, 21% bradycardia, 42% desaturations). In a retrospective study involving 53 infants, transient apnea or bradycardia was observed in 13% of infants following immunization with pentavalent or hexavalent vaccines. Apnea seemed less frequent and less severe following DTaP than wP vaccines [17].

## **6. RESEARCH QUESTION AND OBJECTIVES**

The overall ADVANCE POC question is to test the currently available system for benefit-risk monitoring of vaccines in Europe. There will be several system testing methods, using the following question: Has the initial benefit-risk profile in children prior to school-entry booster been maintained after the switch from wP to aP pertussis vaccines?

The objectives of this specific POC feasibility study, which focuses on the incidence rates of safety outcomes of pertussis-containing vaccines, are:

- 
1. To evaluate participating databases on quality criteria for inclusion in the study (i.e. vaccination data on pertussis vaccine available, at least one of the outcomes available, data access and clearance of protocol possible within timelines of the POC feasibility study)
  2. To provide information that feeds into the benefit/risk model. The safety information required for the model is:  
Incidence rates of specific events (i.e. injection site reactions, fever, somnolence, persistent crying, irritability, febrile or afebrile seizure/convulsion, HHE, extensive limb swelling)
    - a) within specific risk windows after each dose of wP and aP vaccines in pre-school children
    - b) during the period outside the risk windows before and after each dose of wP and aP vaccines in pre-school children.
    - c) Over calendar time, to allow for analysis that will focus on sequential monitoring of B/R
  3. To provide calendar time specific incidence data as test for method development in ADVANCE WP4.

---

[figure not shown]
## 7. RESEARCH METHODS

The overall ADVANCE POC question is to test the currently available system for benefit-risk monitoring of vaccines in Europe. The system will be tested around the following B/R question: Has the initial benefit-risk profile in children prior to school-entry booster been maintained after the switch from wP to aP pertussis vaccines?

### 7.1. Process and methodology for system-testing

Although the system testing will occur largely outside of this study, it is summarised here, with details provided in annexes.

The system testing follows several steps which are visualized in the figure 3 and described in the following chronological order:

**Figure 3 Visualization of the stepwise approach to the system testing**

**Step 1:** Feasibility assessment of the databases: this step will assess whether the quality of the candidate database is sufficient for inclusion in the study. The focus will be on what type of data are available in the databases and whether population, events, and exposure may be misclassified. This step is largely based on the so-called fingerprinting which has been described in deliverable D5.2. A summary of the components and methods is provided in appendix 1. A quality assessment summary will be created per database, with decisions whether the data-sources can or cannot participate in the different pillar studies (see below under 7.2). Responsibility of fingerprinting lies with the workpackage leaders.

**Step 2:** Estimation and delivery of the rates for coverage, benefits and risks, this is described in the different 'pillar' protocols in the databases that may generate adequate results according to the feasibility assessment. Responsibilities are with the study teams that have generated the protocols

**Step 3:** B/R analysis: integration of the incidence rates (generated from step 2) with the utilities to generate a B/R model, as described in the B/R analysis protocol, responsibility with the B/R study team

**Step 4:** Evaluation of the studies and the systems used. This is conducted by a POC evaluation team which is separated on purposes from the POC study teams. A description of the framework for the POC evaluation is attached in appendix 2.

---

This purpose of this protocol is to describe in detail the methods for the risk study in step 2.

## **7.2. Methods for estimations in the scientific question**

### **7.2.1. Design**

This is a retrospective dynamic cohort study to estimate incidence rates of safety outcomes.

A SCCS design will be used to estimate IR ratios for wP vaccines versus baseline periods in databases that capture data on wP vaccinations and will be applied to databases that do not capture data on wP vaccinations to estimate IR in risk windows for those databases.

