Study Design: The main study design is a retrospective dynamic cohort study. The study will be conducted utilizing electronic health care data from ADVANCE partners in different countries (i.e., Short descriptions of databases in respective countries and their full names will be included in this protocol upon final decisions of inclusions). In databases that cover the period in which wP was still provided, the incidence rate (IR) ratio for wP versus baseline risk will be calculated using a self-controlled case series (SCCS) design. This IR ratio will be applied to baseline rates for the aP period in databases that do not capture the wP period, to estimate the rate of events during wP in each specific database.			
Population: The study population will comprise all children registered in any of the participating databases during the study period and for whom an adequate start and end of follow-up and date of birth can be defined. Children will be followed from start of the study period, one month after date of birth (i.e. to allow for pre-vaccination time for the SCCS design and to avoid pre-term related or birth-induced increase in incidence rates), or date of valid data in the database (whichever is the latest) until the end of study period (31-12-2015, the school-entry pertussis booster, transferring out of the database, death, reaching age 6 years: whichever is the earliest).			

**Variables:***Exposure of interest*

Any wP vaccines and aP pertussis-containing vaccines and their doses in the vaccine schedule (D1, D2, D3, D4, D5)

*Outcomes*

- Injection site reactions: erythema, edema, induration/nodule/sterile abscess, pain/tenderness
- Fever
- Somnolence
- Persistent crying, irritability
- Generalized convulsive seizures
- HHE
- Extensive limb swelling

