**Data Sources:**

- Electronic health care databases (record linkage, surveillance and GP-based databases) currently available in the ADVANCE consortium and eligible are located in Denmark, Spain, Italy, The Netherlands and UK. Short descriptions of databases and their full names will be included in this protocol upon final decisions of inclusions.

**Study Size:** Total population (0-6 year of age) of all eligible ADVANCE databases

**Data Analysis:** The purpose of this study is to provide incidence rates (i.e. baseline and risk-window specific) of known adverse reactions following vaccination with pertussis-containing vaccines for use in a multi-criteria decision analysis (MCDA) model of benefits and risks of wP versus aP pertussis vaccines (models are described in a separate benefit-risk study protocol). In some more recent databases, wP information will not be captured. To generate risk-window specific incidence rates for the wP period in these databases, the IR ratio originating from an SCCS analysis of wP versus baseline in other databases will be multiplied by the baseline IR.

**Informed Consent and Ethical Approval:** This study will be conducted on the basis of secondary use of electronic healthcare records. Each database will apply local governance and privacy rules prior to aggregating and sharing anonymized data.

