#### **7.2.5. Population Selection**

The study population will comprise all children registered in any of the participating databases during the study period and for whom an adequate start and end of follow-up and date of birth can be defined. Children will be followed from start of the study period, one month after date of birth (i.e. to allow for pre-vaccination time for the SCCS design and to avoid pre-term related or birth-induced increase in incidence rates), or date of valid data in the database (whichever is the latest) until the end of study period (31-12-2015, the school-entry pertussis booster, transferring out of the database, death, reaching age 6 years: whichever is the earliest). Persons with missing dates of birth or sex will not be included.

For the incidence rate part of the study, we will retain all subjects meeting age and calendar time inclusion criteria with person time greater than zero.

The vaccination day and outcome-specific risk-windows after vaccination will be classified as risk periods, and the period between the end of the risk-window after vaccination until the next pertussis-containing vaccination or end of follow-up as the baseline period. To keep track of dose these periods will also be labeled by the number of previous pertussis-containing vaccinations. For all eligible subjects, CohortStart will be equal to PopulationStart and CohortEnd equal to PopulationEnd.

Databases will be asked to provide dates during which both wP and aP pertussis vaccines were both being used in the population. Patient time during the period of the switch from wP to aP will be removed from the cohort and SCCS analyses to avoid misclassification of exposures.

In order to avoid confounding by infections or other vaccinations, the study population for the incidence rate cohort design will NOT be the same as for the SCCS design.

For the self-controlled case series, analysis sets containing cases of each of the outcomes under study will be defined. For each of these cases, exposure will be defined as: exposed to wP and exposed to aP.

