#### SCCS

A pre-vaccine baseline risk period will be applied to control for the healthy-vaccinee effect. The SCCS will include age in days, and season (classified from the month) as time-varying covariates, as well as all available doses of pertussis vaccine as exposures. Conditional Poisson regression analyses will be conducted for the estimations.

10 describes the availability of wP information of two different databases (i.e. in database [Db] A, wP information is available and in Db B it is not) and the approach how IR within the risk period will be calculated.

**Figure 4: Approach How to Calculate Risk Window Specific IR in Databases where wP Information is Either Available or Lacking**

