### 7.2.9. Limitations

In this POC feasibility study that tests and evaluates the ADVANCE system, tailored to generate rapid evidence on vaccine effects, there are several methodological limitations. These limitations will be assessed, and are an integral part of the system evaluation process. The following points are considered to be the expected limitations:

- Given that this POC feasibility study evaluates a system and its different processes, the epidemiological results produced (i.e. incidence rates and risk ratios) should not be considered as evidence that can be directly translated to inform epidemiological and pharmacovigilance decision-making processes. The epidemiological results produced in this POC feasibility study are part of a set of evaluation indicators to test the ADVANCE system and may not be the best or true estimates
- It could be possible that within the process of database selection it will become evident that proposed case definition(s) for the events are either different, or are differently interpreted, in a specific database or country. Different countries and databases could be using different case definitions. To address this limitation, the study will produce country-and database-specific analyses and results.
- Some event outcomes are signs and symptoms and not disease entities. The coding in databases might not be applicable to signs and symptoms (e.g. crying). Therefore, database extraction algorithms and strategies need to be adapted (e.g. include also free text search).
- Event codes in databases might contain the whole spectrum of potential, probable and confirmed cases. Given the POC feasibility study nature to test the system and to save costs and time, diagnostic codes will not be validated on a patient level using medical histories and charts.

- 
- It is expected that only a limited number of databases will have information on wP vaccination available. Therefore, the suggested strategies in the methods sections 7.4.3 (i.e. multiplying baseline incidence rates with IR ratios across databases, time periods, and wP/ aP data) will be applied. The additional use of literature information will be carefully evaluated and interpreted.
  - The type of database used (e.g. GP database, hospital database, claim database, etc) will influence incidence rates. To address this limitation, the study will produce country/ database-specific analyses and results.

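### The sections disagree on whether the SCCS covers aP, and in databases without wP data the plan sets an SCCS-derived wP rate beside a directly counted aP rate

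*Protocol*

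**What the plan says.** Two descriptions of the SCCS stand side by side.

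- **wP named alone.** Section 7.2.1: "A SCCS design will be used to estimate IR ratios for wP vaccines versus baseline periods in databases that capture data on wP vaccinations". The Abstract (Study Design) gives the same purpose and adds "This IR ratio will be applied to baseline rates for the aP period in databases that do not capture the wP period". The Abstract (Data Analysis) repeats that "the IR ratio originating from an SCCS analysis of wP versus baseline in other databases will be multiplied by the baseline IR".
- **Both vaccines.** Section 7.2.5 says of the SCCS cases: "For each of these cases, exposure will be defined as: exposed to wP and exposed to aP". It goes on to define eligible person-time around any pertussis dose. Section 7.2.8.3 (SCCS) lists the model terms "as well as all available doses of pertussis vaccine as exposures".

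The cohort part of 7.2.8.3 calculates incidence rates directly by vaccine type (wP and aP), dose, risk window, age and calendar year. Multiplying a ratio by a baseline is reserved for databases without wP. The Abstract says "In some more recent databases, wP information will not be captured", and section 7.2.9 adds "It is expected that only a limited number of databases will have information on wP vaccination available".

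**The concern.** A programmer at a database holding only aP cannot tell whether an SCCS is to be run: 7.2.1 implies no, 7.2.5 and 7.2.8.3 imply yes. This decides which estimates exist at all, so it goes beyond analysis detail.

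The second problem follows from the stated design. Where wP is missing, the two vaccines are estimated by different methods, and any systematic difference between the methods appears as a difference between the vaccines. The rates go into a benefit-risk model of wP against aP, and Table 6 in 7.3.1 asks for both under one heading. Section 7.2.9 acknowledges the multiplication across databases but not the mix of estimators.

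**Working it through.** The plan states no figure for this point, so there is none to reproduce. The check sets the two designs side by side and then uses a short identity.

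**Inputs from the protocol (7.2.5)**

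- Cohort baseline: from the end of the risk window to the next pertussis dose or the end of follow-up.
- SCCS baseline: days -31 to -8 before a dose, plus the day after the risk window through day 31.
- Populations: deliberately different. The SCCS uses only children with the event and person-time near doses.

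**Identity**

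Let R_wP and R_aP be the true risk-window rates, B_c the cohort baseline rate and B_s the SCCS baseline rate. Assume perfect transport, that is, the same true rates in the source and target databases.

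1. Imported ratio: IRR_wP = R_wP / B_s.
2. Derived wP rate: B_c × IRR_wP = R_wP × (B_c / B_s) = k × R_wP.
3. aP rate, counted directly in the cohort: R_aP.
4. Contrast as planned: k × (R_wP / R_aP).
5. If aP is also derived as B_c × IRR_aP, it equals k' × R_aP, and the contrast is (k / k') × (R_wP / R_aP). The factor cancels only if k = k'.

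In a database that holds wP, steps 1 and 2 are not used; both rates are direct cohort rates and k does not enter.

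**Illustration**

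The values of k are assumptions, because the protocol gives no baseline rates. The true ratios come from the Dutch questionnaire study cited in section 5: febrile convulsions after dose 4, 0.06% / 0.02% = 3.0; HHE after dose 1, 0.12% / 0.03% = 4.0.

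| assumed k | convulsions (true 3.0) | HHE (true 4.0) |
|---|---|---|
| 0.5 | 1.5 | 2.0 |
| 0.8 | 2.4 | 3.2 |
| 1.0 | 3.0 | 4.0 |
| 1.25 | 3.75 | 5.0 |
| 2.0 | 6.0 | 8.0 |

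With the same method for both vaccines and k = k', the contrast stays at 3.0 and 4.0 throughout.

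**On the difference scale**

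Take convulsions with k = 1.25. The true difference is 0.06 - 0.02 = 0.04 percentage points.

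- As planned: 0.075 - 0.02 = 0.055, which is 37.5% too high.
- Both vaccines derived: 0.075 - 0.025 = 0.05, which is still 25% too high.

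Using one method for both vaccines removes k from a ratio but not from a difference.

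**The case against.** The strongest reply is that the sections describe different things. Sections 7.2.5 and 7.2.8.3 define the model, with both vaccines in it; 7.2.1 and the Abstract say which ratio is exported. Nothing excludes aP from the SCCS. This reading is possible, but the protocol does not state it, and it leaves open whether aP ratios are reported or used.

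Figure 4, on calculating rates with and without wP information, is not reproduced in the text at hand and may show how aP is handled. That aP stays a direct cohort rate in databases without wP is therefore inferred from 7.2.8.3.

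It is also true that no hypothesis is tested, that the contrast itself is made in a separate benefit-risk protocol, and that 7.2.9 warns against using the results for decisions. None of this removes a method difference from the rates delivered.

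Three stronger readings are tempting, and the documents do not support them.

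- *All wP rates are modelled and all aP rates are crude.* Databases with wP give direct wP rates, and the cohort rates are stratified by age and calendar year.
- *wP is overstated by a known percentage, because the pre-vaccination baseline is depleted of events.* No depletion figure is given, and days -7 to -1 are already left out of the baseline, so even the direction is open.
- *Running the SCCS for both vaccines removes the bias.* The wP ratio would still be imported while the aP ratio is local, so transport error remains. Cancellation also needs equal bias for both vaccines and a ratio scale.

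**Conclusion.** The concern holds within limits. The scope of the SCCS is described inconsistently and must be reconciled. In databases without wP, which 7.2.9 implies will be most of them, the wP-aP contrast carries a factor k = B_c / B_s on the wP side only, because the two designs differ in baseline time and population. Its size and direction cannot be obtained from the documents; the table shows only how k passes into the contrast. The identity assumes perfect transport of the ratio, and imperfect transport would add a separate error. Databases that hold wP are not affected. The point should be addressed before the analysis, because the planned analysis contains no check on the product method on which many wP rates will rest.

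**What to change.** 1. Reconcile 7.2.1, the Abstract (Study Design and Data Analysis), 7.2.5 and the SCCS part of 7.2.8.3. State that the SCCS is run for wP and for aP in every database holding the respective vaccine, which ratios are reported, and which one is exported.
2. Keep the observed aP rate as the main figure. Replacing it with a derived one would put k into a rate that was counted directly.
3. In each database without wP, also report aP as its SCCS ratio times the same baseline, next to the observed aP rate. Give the wP-aP contrast on this like-for-like basis as a sensitivity analysis. Derived aP divided by observed aP estimates the factor for aP in that database.
4. In databases with wP, compare the product-based wP rate with the observed wP rate.
5. State that these comparisons check method bias shared by the two ratios, and not whether the wP ratio transports between databases.

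The cost is one more model run per outcome and a second set of aP figures to present. No new data are needed, since aP doses and events are already extracted for the cohort analysis.
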